6.8 Subject Death

6.8.1 Procedure for recording and reporting Subject Death

The investigator will document and report all subject deaths to the sponsor immediately but no later than 72 hours after becoming aware of the event.

Should death occur, the investigator should record the information in the hospital records and immediately document the information on the Death Form. By completing the form the sponsor will be notified.

Note: Refer to Table 1 'Data Collection' and Appendix D 'Data Collection Method'. In case of EDC failure, notify Sponsor via fax ([contact]) or e-mail ([contact]).

Subject Death is the outcome of a serious adverse event (SAE). Death can therefore be related to an SAE and all efforts to obtain the SAE details should be made and the Adverse Event form must be completed. Any supporting documentation (autopsy records, death certificates, hospitalization records) must be sent to SJM with the corresponding SAE and Death CRFs. Prior

to sending such documentation, personal identifiers will be redacted and replaced by the study-specific subject ID.

The subject's death is an Early Conclusion of the subject's participation in the investigation. Therefore, the investigator is requested to complete the Termination form.

The investigator must notify the EC, if appropriate, in accordance with national and local laws and regulations.

6.9 Document and data control

6.9.1 Traceability of documents and data

The investigator shall ensure accuracy, completeness, legibility and timeliness of the data reported to the sponsor on the electronic case report forms (eCRFs) and in all required reports. When copies of the original source document as well as print outs of original electronic source documents are retained, these shall be signed and dated by a member of the investigational site team with a statement that it is a true reproduction of the original source document.

6.9.2 Recording data

Source documents shall be created and maintained by the investigational site team throughout the clinical investigation.

The data reported on the eCRFs shall be derived from, and be consistent with, source documents, and any discrepancies shall be explained in writing.

The eCRFs shall be validated and signed by the Principal Investigator or a delegated investigator. Any change or correction to data reported shall be dated and explained if necessary. The original entry will remain available by audit trail.

6.9.3 Review of data

The clinical investigation will be monitored by reviewing the eCRF approved by the investigators.

The following activities will occur:

- eCRFs will be reviewed for completeness and accuracy after being uploaded into the database.
- The investigator (co-investigator) and/or delegate is notified regarding any missing or unclear/inconsistent data.

6.10 Monitoring

Risk-based monitoring shall be performed during the clinical investigation in order to guarantee adherence to all applicable regulations, the Clinical Investigation Plan and the signed Clinical Study Agreement. By monitoring, the Sponsor can also verify the accuracy of data collected on the accompanying eCRFs throughout the duration of the clinical investigation.

Monitoring is necessary to ensure adequate protection of the rights and safety of human subjects involved in the clinical investigation and the quality and integrity of the data obtained during the investigation. The sponsor will at the same time assess the investigational site and study team on staffing and facilities to ensure the investigation can continue in a safe and effective fashion.

During the monitoring visits, data reported on the eCRF shall be reviewed as specified in the monitoring plan.

6.10.1 Designated Monitors

Only monitors qualified by education, training and experience, which have been trained on the Clinical Investigation Plan, eCRF content, Monitoring Plan, relevant requirements and informed consent process will be allowed to perform monitoring activities during this clinical investigation. The monitor's qualifications and training will be documented by the sponsor. A list of monitors is available upon request.

6.10.2 Monitoring Plan

Prior to the start of the site monitoring activities for this clinical investigation, a project specific Monitoring Plan (MP) will be created.

At a minimum, the Monitoring Plan will include the following:

- Required activities
- Frequency of monitoring visits
- Visit Requirements
- Procedures for securing site compliance
- Monitoring report content and timelines
- Close-out procedures

The Monitoring Plan may be updated as appropriate. All revisions will be tracked.

6.11 Competent Authority (CA) Inspections

The investigator and/or delegate should contact SJM immediately upon notification of a CA inspection at the site. A clinical representative will assist the investigator and/or delegate in preparing for the inspection.

An investigator who has authority to grant access shall permit authorized CA employees, at reasonable times and in reasonable manner, to enter and inspect any establishment where devices are held (including any establishment where devices are used or where records or results are kept).

An investigator, or any person acting on behalf of such a person with respect to the investigation, shall permit authorized CA employees, at reasonable times and in reasonable manner, to inspect and copy all records relating to the investigation.

An investigator shall permit authorized CA employees to inspect and copy records that identify subjects, upon notice that CA has reason to suspect that adequate informed consent was not obtained, or that reports required to be submitted by the investigator, to the Sponsor or EC have not been submitted or are incomplete, inaccurate, false or misleading.

6.12 Investigation Termination

The Sponsor reserves the right to suspend or terminate the investigation in an individual site or the entire clinical investigation for significant and documented reasons, at any stage, with appropriate written notice to the investigator.

The investigation will be terminated according to applicable regulations.

At termination, the investigator shall return all documents to the sponsor, and notify the Ethics Committee and the Competent Authority (where applicable). Follow-up for all enrolled subjects will be continued as per standard of care.

6.12.1 Resuming the Clinical Investigation after Suspension

The sponsor shall conclude an analysis of the reason(s) for the suspension, implement the necessary corrective actions, and decide to lift the temporary suspension. The sponsor shall inform the Principal Investigators, EC/Head of Medical Institution or regulatory authority, where appropriate, and the regulatory authority of the rationale, providing them with the relevant data supporting this decision.

Concurrence shall be obtained from the, EC/Head of Medical Institution or regulatory authority where appropriate, before the clinical investigation resumes.

If subjects have been informed of the suspension, the Principal Investigator or authorized designee shall inform them of the reasons for resumption.

6.12.2 Investigation Conclusion

The investigation will be concluded when:

- A Close Out visit has been performed at each participating site AND
- The final report has been provided by the sponsor.

7 Risks and Benefits of the clinical investigation

7.1 Anticipated clinical benefits

It is expected that subjects undergoing a renal denervation procedure with the EnligHTN Renal Denervation System will experience additional and sustainable blood pressure lowering effects compared to drug treatment alone.

The information collected in this clinical investigation will be added to the current knowledge and understanding of treatment options for patients with uncontrolled hypertension.

7.2 Anticipated Adverse Events and Adverse Device Effects

Adverse events potentially associated with the use of the EnligHTN Renal Denervation System and their potential complications are documented in the Instructions for Use (IFU) which is available upon request.

7.3 Steps that will be taken to control or mitigate the risks

No additional risks above those known for the device are to be expected in this observational study. Following efforts to minimize risks will be taken:

- Regular clinical investigation monitoring visits with risk-based monitoring of collected patient data across all centers.
- Conduction of the clinical investigation in accordance with the Clinical Investigational Plan (CIP), all applicable laws and regulations and any conditions of approval imposed by the appropriate EC or applicable regulatory authorities where the clinical investigation is performed.

- Preparation of the catheter and performance of the renal denervation procedure in accordance with the device IFUs.
- Catheter advancement under fluoroscopic imaging to minimize the risk of arterial damage.
- Training of Investigators both on the CIP and the EnligHTN Renal Denervation procedure.

7.4 Risk-to-benefit rationale

The risks associated with the EnligHTN Renal System are comparable to those associated with the use of other currently available renal denervation systems. Patients participating in this clinical investigation are indicated for a renal denervation procedure as part of their standard medical management and are subject to the risks associated with these devices. It is considered that renal denervation offers a better long-term prognosis which should fairly outweigh the potential risk associated with such procedure.

8 Statistical considerations

8.1 Study design

This is a post market, prospective, observational study of the EnligHTN™ Renal Denervation System. Approximately 500 subjects with uncontrolled hypertension will undergo renal artery ablation at approximately 50 investigational sites located in Europe and the Middle-East and will be followed up to 1 year post procedure.

The primary objective is to evaluate a mean reduction of office Systolic Blood Pressure at 6 months post renal denervation.

8.2 Sample size estimation

The sample size estimation is based on the primary objective of this study. The aim is to define a precise two sided 95% confidence interval with a half width of 2.35mmHg for the mean reduction of office SBP at 6 Months. Using estimates from the EnligHTN 1 study, the mean \pm SD for reduction of office SBP at 6 Months was -26 ± 24.7 mmHg. In order to achieve the desired level of precision a total of 425 patients is needed. Assuming a 15% attrition rate the study will aim to enroll approximately 500 patients.

8.3 Analysis Population

All patients who have signed a Patient Informed Consent (PIC) will be considered enrolled in the study. However, Primary Analysis population will include those patients that have signed a PIC form, and had the EnligHTN™ Renal Denervation System enter his/her body. The sample size of 500 subjects refers to those subjects in the Primary Analysis population.

As Treated population will include all subjects in whom renal denervation was performed in a minimum of one renal artery per kidney (according to the Instructions for Use).

It is anticipated that there may be subjects who have been enrolled in the study but are not included in the Primary Analysis population or As Treated population, such as:

- Subjects who are enrolled but do not meet baseline inclusion or exclusion criteria before the procedure; these are considered the screen failure population.
- Procedurally excluded populations will include subjects who have enrolled in the study and start the procedure, but do not have the EnligHTN™ Renal Denervation System enter his/her body, due to their anatomy, circumstances related to the procedure, or physician judgment.

Subjects who withdraw from the investigation will not be replaced in any analysis population.

8.4 Data Analysis and Reporting

Data analysis will be performed across all subjects, based on Primary Analysis population unless otherwise specified.

The data collected will be presented using the appropriate summary statistics. Continuous data will be summarized using descriptive statistics (number of observations, mean, standard deviation, minimum and maximum values).

Continuous primary and secondary outcomes between time points will be compared as follows: normality of data will be verified with the use of box plots and Kolmogorov-Smirnov normality tests. For normally distributed data, comparisons will be performed using paired t-tests. In cases

CV-12-064-EU-HT_CIP_V2.0_final_25Mar2014 EnligHTN European Observational Study

©2014 – SJM International, Inc.: All rights reserved. No portion of this work may be reproduced in whole or in part without the express written permission of SJM International, Inc.

where the data is not normally distributed, the non parametric Wilcoxon-Signed-Rank test will be used to analyze the data. Results will be expressed in terms of p-values. Categorical data will be summarized using frequencies and percentages.

8.4.1 Primary objective analysis

The mean reduction of office SBP at six (6) months of the study will be analyzed by:

1. Computing the reduction of SBP measurements at 6 months compared to baseline for each patient with data available in both time points.
2. Calculating the mean and standard deviation of the SBP reduction at 6 months

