5.5 Clinical Investigation Termination

Each subject will be followed for 1 year post renal denervation procedure or until time of death, loss of follow up, withdrawal or clinical investigation termination. The clinical investigation will be complete after all follow-up visits are performed, all data is received by the Sponsor and the database is locked. The study will be closed when a final report is written on the conclusions and analysis of the data.

Participation in this clinical investigation is voluntary. Subjects are free to withdraw from the clinical investigation at any time without reason. A Clinical investigation Termination CRF should be completed by the site and provided to the Sponsor.

In a situation where a clinical investigation withdrawal is due to an adverse event the subject should be followed until resolution of that adverse event or determination that the subject's condition is stable.

Subjects must be informed about their right to withdraw from the investigation at any time and for any reason without sanction, penalty or loss of benefits to which the subject is otherwise entitled and withdrawal from the investigation will not jeopardize their future medical care or relationship with the investigator. Subjects will be asked to specify the reason for the termination, but have the right not to answer.

The investigator may decide to withdraw a subject from the investigation at any time. The subject's future care will not be influenced by a decision, voluntary or otherwise, to withdraw from the investigation. All reasonable efforts should be made to retain the subject in the clinical investigation until completion of the investigation.

Other reasons for termination or withdrawal include, but are not limited to, the following:

- Subject did not meet the inclusion/exclusion criteria
- Subject death (in case of subject death, the cause must be documented)
- Subject and/or family request
- Subject non-compliance
- Subject lost to follow-up, defined as the following: a subject will be considered "lost to follow-up" after a minimum of 2 documented phone calls of a physician or delegate at the study site to the subject or emergency contact and a certified letter sent to the last known address
- Subject's participation terminated by Investigator
- Study terminated by SJM
- The study terminated according to locally applicable regulations

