8.4.2 Secondary objectives analysis

Acute (30 days post procedure)

- Safety
The percentage of subjects with peri-procedural events within 30 days post procedure will be computed as follows:

$$\frac{\text{Number of subjects with peri procedural events within 30 days post procedure}}{\text{Number of subjects that underwent the procedure}} * 100$$

- Performance
The mean reduction in office Systolic and Diastolic Blood Pressure at 1 month and the mean reduction in ambulatory Systolic and Diastolic Blood Pressure at 1 month will be calculated in a similar way as described for the primary objective (Section 8.4.1). The percentage of subjects achieving office Systolic Blood Pressure < 140 mmHg at 1 month will be computed as follows:

$$\frac{\text{Number of subjects achieving office SBP < 140 at 1 month}}{\text{Number of subjects with data available at 1 month}} * 100$$

Mid to long term (6 and 12 months)

- Safety
Renal function change based on eGFR will be summarized by:
 1. Computing the change of the eGFR at 6 and 12 months, compared to baseline for each patient with data available at both time points.
 2. Calculating the mean and standard deviation of the eGFR change at those intervals

Assessment of renovascular safety as measured by occurrence of new renal artery stenosis (> 50%) and aneurysm at the site of ablation per Renal Artery Imaging will be summarized at 6 months as a percentage of subjects who have stenosis (> 50%) or aneurysm.
- Performance

The mean reduction in office Systolic Blood Pressure at 12 months, the mean reduction in office Diastolic Blood Pressure at 6 and 12 months and the mean reduction in ambulatory Systolic and Diastolic Blood Pressure at 6 and 12 months post denervation will be calculated in a similar way as described for the primary objective (Section 8.4.1).

Percentage of subjects achieving office Systolic Blood Pressure < 140 mmHg at 6 and at 12 month will be computed as follows:

$$\frac{\text{Number of subjects achieving office SBP} < 140 \text{ at 6 months}}{\text{Number of subjects with data available at 6 months}} * 100$$

$$\frac{\text{Number of subjects achieving office SBP} < 140 \text{ at 12 months}}{\text{Number of subjects with data available at 12 months}} * 100$$

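### The 6-month office SBP reduction and <140 mmHg rate rest on an available-case rule that no planned analysis tests, although 8.2 assumes 15% attrition from the roughly 500 subjects in the Primary Analysis population

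*Combined protocol and SAP*

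**What the plan says.** Section 8.3 states that the "Primary Analysis population will include those patients that have signed a PIC form" and in whom the system entered the body. It adds: "The sample size of 500 subjects refers to those subjects in the Primary Analysis population". Section 8.4 makes this the default analysis set. Section 8.2 derives 425 evaluable patients and continues: "Assuming a 15% attrition rate the study will aim to enroll approximately 500 patients".

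Section 8.4.1 then defines the primary result by "Computing the reduction of SBP measurements at 6 months compared to baseline for each patient with data available in both time points", followed by the mean and SD. In 8.4.2 the denominator of the 6-month <140 mmHg rate is "Number of subjects with data available at 6 months".

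Under 5.5, subjects are followed for one year "or until time of death, loss of follow up, withdrawal or clinical investigation termination". The same section says "The investigator may decide to withdraw a subject from the investigation at any time" and lists "Subject non-compliance" among the reasons, without saying what kind. It also asks for retention efforts, a termination form and the reason for leaving, which the subject may decline to give. Subjects withdrawn for an adverse event are followed until it resolves or stabilises, but no SBP visit is promised. Section 4.5 requires withdrawn and lost subjects to be logged.

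Section 8.4 summarises continuous data by number of observations, mean, SD and range, categorical data by frequencies and percentages, and comparisons by p-values. Section 8.4.3 offers medication summaries, optional subgroups, optional As Treated analyses and unspecified ad hoc analyses.

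**The concern.** The analysis set has about 500 members, but under the plan's own assumption the primary result would describe about 425 of them. That is harmless if the missing subjects respond like those seen. Section 8 neither states nor examines that condition; attrition enters only to raise N.

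A link between response and loss is possible here. The study is open label without a control arm, and the investigator who sees the blood pressure may withdraw the subject. If poor responders are missing more often, both the mean reduction and the control rate look too favourable, and no between-group comparison offsets it. The stated aim in 8.2 is a precise interval for this mean, and precision computed from the subjects seen says nothing about selective loss.

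Office SBP is scheduled at 1 and 12 months (Table 1; 5.4.2), so many subjects without a 6-month value would still have informative readings. The plan does not use them for the 6-month estimate.

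**Working it through.** **Inputs.** From 8.2: 6-month change −26, SD 24.7 mmHg; half-width 2.35; 425 evaluable; 15% attrition (taken as loss by 6 months, since 8.2 sizes on that endpoint). From section 3: 1 of 46 missing at 6 months, 1-month change −28, and up to 41% below 140 mmHg over follow-up. All dropout contrasts, the normal distributions, the 1-month SD (set to 24.7) and the 1-month/6-month correlation are assumptions.

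**The plan's figures reproduce.** (1.96 × 24.7 / 2.35)² = 424.4, rounded up to 425. 425 / 0.85 = 500. 500 × 0.15 = 75 missing. The half-width at 425 is 1.96 × 24.7 / √425 = 2.35.

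**Simple bound.** Bias of the available-case mean = missing share m × (mean reduction in those seen − mean reduction in those missing). At m = 0.15 a gap of 5 mmHg gives 0.75. A gap of 26 (no missing subject improves on average, an extreme) gives 3.9. The bias equals 2.35 when the gap is 2.35 / 0.15 = 15.7. With gaps capped at 26, it can reach 2.35 only if at least 2.35 / 26 = 9.0% are missing (46 of 500).

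**Dropout contrast, driven by the 6-month response.** Subjects with <10 mmHg reduction drop out r times as often as the others, with the total m held fixed.
- P = P(reduction < 10) = 1 − Φ(16 / 24.7) = 0.259.
- The mean changes of the two groups differ by 24.7 × φ(0.648) × (1/0.259 + 1/0.741) ≈ 41.7 mmHg.
- Dropout in the others: q = m / (1 + (r − 1)P). In poor responders: a = rq.
- Bias = 41.7 × P × (a − m) / (1 − m).

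| Missing | r | a v q | Bias, mmHg |
|---|---|---|---|
| 15% | 1 | 15% v 15% | 0 |
| 15% | 1.5 | 19.9% v 13.3% | 0.62 |
| 15% | 2 | 23.8% v 11.9% | 1.12 |
| 15% | 3 | 29.7% v 9.9% | 1.86 |
| 5% | 3 | 9.9% v 3.3% | 0.55 |
| 2.2% (1 of 46) | 3 | 4.3% v 1.4% | 0.23 |

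**Driven by the 1-month response.** The same formula is applied to a 1-month change of N(−28, 24.7), and the result is multiplied by the correlation. With correlation 0.5 and 15% missing, the bias is 0.54 (r = 2) and 0.91 (r = 3). For correlations of 0.3 to 0.7 it is 0.32 to 0.76 and 0.55 to 1.27.

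**What the 1-month data recover.** In a simulation of 2 million subjects (15% missing, correlation 0.5, regression of 6-month on 1-month change), a 1-month driver gives −25.98 (r = 2) and −26.01 (r = 3), so the bias is removed. A 6-month driver gives −26.83 and −27.44, leaving 0.83 and 1.44. A model on earlier readings is therefore not enough alone.

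**Control rate.** Taking 41% among those seen and counting missing as not controlled: 0.41 × 0.85 = 34.9% at 15% missing, and 0.41 × 45/46 = 40.1% at 1 of 46.

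**The case against.** The study is single arm, post market and descriptive, with no success threshold. The available-case rule and its denominators are stated openly. The 15% is a planning allowance, and the only missingness documented is 1 of 46, where the bias is about 0.2 mmHg even at a ratio of 3. Every dropout contrast above stays below 2.35 mmHg. All of this stands and limits the priority.

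Three further points also stand.
- The general summary rule in 8.4 would show the 6-month number of observations and probably the withdrawal reasons, so a reader would see how many are missing. What is absent is earlier SBP by 6-month data status and any sensitivity analysis.
- The 95% interval appears only in the sizing section; 8.4 lists none. The 2.35 mmHg is therefore a yardstick for size, not a planned output that would be wrong.
- Permission for ad hoc analyses allows a sensitivity analysis. It does not plan one, and an analysis chosen after the data are seen carries less weight.

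A reader might infer that the sample size is wrong. It is not: it reproduces and already allows for the loss. A reader might also infer that the wording in 5.1.5 on excluding non-compliant subjects removes them from the analysis. That sentence does not say from what they would be excluded, and it does not change the set defined in 8.3.

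**Conclusion.** The omission is real, and correcting it is a cheap improvement of minor to moderate priority. The plan prespecifies an available-case rule for the 6-month mean and control rate, assumes a loss of about 75 subjects, and neither tests the rule nor uses the other SBP readings for the 6-month estimate.

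The size rests on assumed dropout contrasts. At 15% missing with ratios of 1.5 to 3 on the 6-month response, bias is about 0.6 to 1.9 mmHg. With ratios of 2 to 3 on the 1-month response (correlation 0.5), it is about 0.5 to 0.9 mmHg. It is zero if loss is unrelated to response, and about 0.2 mmHg at 1 of 46 missing with a ratio of 3.

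A reader might go further and conclude that the reported reduction will be overstated, or that 15% will in fact be lost. The documents support neither. They contain no response data for withdrawn subjects, so direction and size are unknown, and 15% is an assumption.

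**What to change.** 1. **Section 8.4.1.** Keep the available-case mean. Beside it, report the 6-month change with 95% CI from a prespecified repeated-measures mixed model of office SBP (baseline, 1, 6 and 12 months; visit as fixed effect; unstructured covariance) on all Primary Analysis subjects. State whether the discharge reading is used; leaving it out is simplest. Report deaths before 6 months separately and state how they enter the model.
2. **Delta sensitivity analysis.** Worsen the imputed missing 6-month values over a stated range, for example 0 to 26 mmHg, and report the mean at each step. Exclude deaths or handle them as stated in item 1. This is needed because the model does not remove bias when loss depends on the unseen 6-month value. Below about 9% missing, no delta in that range shifts the mean by 2.35 mmHg, and the report should say so if that applies.
3. **Section 8.4.2.** Also report the <140 mmHg rate with missing counted as not controlled, labelled a lower bound. Tabulate baseline and 1-month SBP by 6-month data status.

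**Cost.** These are standard SAS analyses of data already scheduled. N stays at 425/500. Section 11 requires a plan amendment, with ethics committee notification or approval where required. No visit changes, so the re-consent rule should not be triggered. The downside is a little more analysis and possibly a slightly less favourable estimate.

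Separately, the exclusion wording in 5.1.5 should be reconciled with 5.5 and 8.3. That is a clarification and not part of this point.
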